4.1 Phase II Study Assessment Tables

 Initial Study Assessments Table 												
*Evaluations are completed weekly, every 7 days ± 3 days												
Nu-V3 Treatment Arm Evaluation*	Week 1	Week 2	Week 3	Week 4	Week 5	Week 6	Week 7	Week 8	Week 9	Week 10	Week 11	Week 12
Informed Consent	x											
Inclusion and Exclusion ¹	x											
Patient Registration ¹	x											
Medications Form ¹	x			x				x				x
Patient Onboarding and Orientation ²	x											
In office assessment	x	x	x	x	x	x	x	x	x	x	x	x
New Device Placed ³	x				x				x			
Pad Replaced ³		x	x	x		x	x	x		x	x	x
Treatment Forms ¹	x	x	x	x	x	x	x	x	x	x	x	x
No Device												
HRV Assessment (optional) ⁴	x	x	x	x	x	x	x	x	x	x	x	x
ePRO Questionnaires ⁵	x	x	x	x	x	x	x	x	x	x	x	x
Patients' Global Impression of Change ePRO form (PGIC) ⁵		x	x	x	x	x	x	x	x	x	x	x
Providers' Global Impression of Change ePRO form (PGIC) ¹		x		x		x		x		x		x
Optional Patient Media Testimony ⁶	x	x		x				x				x

1. Inclusion/Exclusion, Registration, Medications, Treatment, and Providers' PGIC forms to be completed by site via online module.
2. Patient Onboarding and Orientation includes introductory demographics form, Nu-V3 patient training video
3. Upon having three consecutive weeks of primary symptom reduction of $\geq 70\%$ via patient reported numerical scales from baseline, the participant will have reached symptom response plateau and will continue as described in the study assessments table, but without device therapy. Then if the participant's primary symptom score increases at any time by $\geq 20\%$ from the symptom response plateau, they may again continue device therapy until week 24.
4. (Optional) HRV assessment will be conducted before the first treatment and again 15-20 minutes following the first treatment. The HRV assessment will also be conducted prior to each weekly treatment. This assessment is applicable to participating sites per the clinical trial agreement. Contact the clinical trial manager for Information.
5. ePRO questionnaires completed on patient's mobile device: DQ-9 (baseline), PTB-7, PEG, GAD-7, PHQ-9, PROMIS 4a, PGIC
6. If patient consents to media testimony, site will collect via study collection process.

Nu-Life Solutions Miniaturized Wearable Medical Technology - NuJ ³	Study Assessments Table											NuJ ³
	*Evaluations are completed weekly, every 7 days ±3 days											

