Nu-V3 Treatment Arm Evaluation*	Week 13	Week 14	Week 15	Week 16	Week 17	Week 18	Week 19	Week 20	Week 21	Week 22	Week 23	Week 24
Medications Form ¹				x				x				x
In office assessment	x	x		x	x		x	x		x	x	x
New Device Placed ²	x			x			x			x		
Pad Replaced ²		x			x			x			x	
Treatment Forms ¹	x	x		x	x		x	x		x	x	
No Device			x			x			x			x
HRV Assessment (optional) ³	x	x		x	x		x	x		x	x	
ePRO Questionnaires ⁴	x	x	x	x	x	x	x	x	x	x	x	x
Patients' Global Impression of Change ePRO form (PGIC) ⁴	x	x	x	x	x	x	x	x	x	x	x	x
Providers' Global Impression of Change ePRO form (PGIC) ¹		x			x			x		x	x	
Optional Patient Media Testimony ⁵	x	x		x				x				x

1. Providers' PGIC form, Medications and Treatment forms to be completed by site via online module.
2. Upon having three consecutive weeks of mean symptom reduction of ≥70% via patient reported numerical scales, the participant will continue as described in the study assessments table, but without device therapy. Then if the participant's primary symptom score increases at any time by ≥20%, they may again continue device therapy until week 24.
3. (Optional) HRV assessment before the first treatment and again 15-20 minutes following the first treatment. HRV assessment will also be conducted prior to each weekly treatment. This assessment is applicable to participating sites per the clinical trial agreement. Contact the clinical trial manager for information.
4. ePRO questionnaires completed on patient's mobile device: DQ-9 (baseline), PTB-7, PEG, GAD-7, PHQ-9, PROMIS 4a, PGIC
5. If patient consents to media testimony, site will collect via study collection process.

Nu-Life Solutions Miniaturized Wearable Medical Technology - NuJ ³	Control Study Assessments Table											NuJ ³
	*Evaluations are completed weekly, every 7 days ±3 days											
Control Arm Evaluation*	Week 1	Week 2	Week 3	Week 4	Week 5	Week 6	Week 7	Week 8	Week 9	Week 10	Week 11	Week 12
Informed Consent	x											
Inclusion and Exclusion ¹	x											
Patient Registration ¹	x											
Medications Form ¹	x			x				x				x
Patient Onboarding and Orientation ²	x											
In office assessment	x			x				x				x
No Device	x	x	x	x	x	x	x	x	x	x	x	x
ePRO Questionnaires ³	x			x				x				x
Patients' Global Impression of Change ePRO form (PGIC) ³				x				x				x

1. Inclusion/Exclusion, Registration, Medications, Treatment, and Providers' PGIC forms to be completed by site via online module.

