8.0 STUDY ENDPOINT and DATA ANALYSIS

8.1 Primary Endpoints: Primary endpoints consisted of the following:

Safety: At screening/baseline, a medical history will be obtained to capture relevant underlying conditions. The screening/baseline examinations will include BP, and HR. Baseline signs and symptoms are those that are assessed within 14 days prior to week 1 treatment.

Concomitant medications will be collected from within 14 days prior to enrollment through the study treatment period and maintenance period (see Study Assessments Table section 4.1).

The primary safety endpoint is the occurrence of reported unanticipated problems involving risk to subjects or others (“UPIRTSOs”). These UPIRTSOs are defined as those problems which alter the risks to subjects or others. This includes any study suspensions or holds. The primary safety endpoint analyses will be based on a risk-benefit conclusion.

Effectiveness: There are four instruments measuring participant’s symptoms of chronic pain, anxiety, depression, and sleeplessness. The primary effectiveness endpoint is a statistically significant reduction in one or more of measures of: chronic pain, anxiety, depression, or sleeplessness between baseline and 12 or 24 weeks after initiating treatment.

The null hypothesis to disprove is that there is no statistically significant reduction from baseline to 12 or 24 weeks in mean chronic pain, anxiety,

depression, or sleeplessness symptom severity scores using the Nu-V3 device compared with the usual care cohort.

The instruments used in this study are:

Chronic Pain – Pain intensity (P), interference with enjoyment of life (E), and interference with general activity (G) (PEG Scale),

The PEG is a three-item instrument that measures pain intensity (one item) and pain interference (two items). Each item is valued from 0 (no pain/interference) to 10 (as bad as you can imagine). The instrument score is calculated as the average of the three item values.

Anxiety - Generalized Anxiety Disorder 7-item (GAD-7)

The GAD-7 is a seven-item instrument that measures respondents' symptoms of anxiety. Each item is scored on a four-point Likert scale, and values range from 0 ("Not at all") to 3 ("Nearly every day".) Items are summed to determine the instrument's score. Values of 10 or higher have been associated with moderate anxiety, while values of 15 or higher have been associated with severe anxiety.

Depression - Patient Health Questionnaire (PHQ-9)

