The PHQ-9 is a nine-item instrument that measures depression-related symptoms and functional impairment. Each item is scored on a four-point Likert scale and values range from 0 ("Not bothered at all") to 3 ("Bothered nearly every day.") The items' values are summed to determine the instrument's score. PHQ-9 values of 10 and 15 represent moderate and moderately severe depression respectively.

Sleeplessness - PROMIS short form 4a

This eight item instrument measures sleep disturbance and sleep-related impairment.

8.2 Secondary Endpoints: Secondary endpoints consisted of the following:

Effectiveness: There are two secondary effectiveness endpoints:

1. In the Nu-V3 device treatment arm, the study will report the mean time from treatment initiation to reduction of symptoms of at least 30% in any of the four domains of symptom measurement.
2. In both the Nu-V3 device treatment arm and the observation arm, the study will report the mean percentage change in symptoms severity from initiation to 12 and 24 weeks for each instrument.

Additional secondary endpoints of this study are:

- Mean improvement in quality of life measured with Patient's Global Impression of Change (PGIC) between the treatment and usual care arm, and

- Mean improvement in activities of daily living via Perceived Treatment Benefit Form (PTB-6) between the treatment and usual care arm.

8.3 Sub-Analyses: Sub-Analyses consist of the following:

The study has several sub-analyses. They include:

- The mean number of weeks that chronic pain, anxiety, depression, and sleeplessness response are achieved and sustained, without utilization of another device or change in other treatments, during the full 24-week intervention in the Nu-V3 device treatment arm.
- The mean number of weeks to initial benefit from Nu-V3 device use in the Nu-V3 device treatment arm. Benefit is defined as a reduction of at least 30% of symptoms in at least one of chronic pain, anxiety, depression, or sleeplessness.
- **The device's comfort-of-use, and patient's perceived treatment benefit** in the Nu-V3 device treatment arm.

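### The time-to-30%-improvement endpoint is fixed as a plain device-arm mean, which has no value for participants who never improve by 30%, and no 30% response figure is planned for controls

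*Protocol*

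**What the plan says.** Section 8.2, item 1, is limited to the Nu-V3 arm and states that "the study will report the mean time from treatment initiation to reduction of symptoms of at least 30% in any of the four domains". The second bullet of section 8.3 gives the same quantity as a mean number of weeks to initial benefit, again in the device arm only: "Benefit is defined as a reduction of at least 30% of symptoms in at least one of chronic pain, anxiety, depression, or sleeplessness". The statistic, the event and the arm are therefore all fixed in the protocol.

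Three other analyses bear on the point:
- The first bullet of 8.3 covers durability in the device arm: "The mean number of weeks that chronic pain, anxiety, depression, and sleeplessness response are achieved and sustained".
- Item 2 of 8.2 reports, for both arms, the "mean percentage change in symptoms severity from initiation to 12 and 24 weeks for each instrument".
- The null hypothesis in 8.1 concerns "symptom severity scores using the Nu-V3 device compared with the usual care cohort".

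None of these is a 30% response figure for the control arm.

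On timing, the device-arm tables in section 4.1 carry the note "Evaluations are completed weekly, every 7 days" and mark the ePRO questionnaires at every week from 1 to 24. The table headed "Control Study Assessments Table" marks the same questionnaires at weeks 1, 4, 8 and 12. Section 3.1 sets one severity floor: 5 out of 10 for the primary symptom, on a separate Baseline Symptom Questionnaire.

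**The concern.** There are two difficulties.

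First, a mean time to an event exists only if everyone has the event. Some participants will probably never show a 30% fall, and the protocol's statistic gives them no value. The easy way out is to average those who did respond. That answers how quickly responders responded, and says little about how many there were. A device that helps few people could then be reported with a time not far from that of a device that helps many.

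Second, the event needs only one reading, in one of four domains, at one of many weekly assessments. Scores of stable people fluctuate. Three of the four domains have no entry severity requirement, and in a domain that starts low a 30% fall can be a single point. At a GAD-7 or PHQ-9 baseline of 3, one point is 33%. Some apparent benefit will arise without any device effect, and the plan places no control-arm figure beside it.

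**Working it through.** The protocol gives no expected response rate, time, SD or reliability for this endpoint, so there is no figure of its own to reproduce. What follows is illustration on stated assumptions.

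**1. Assessments.** From section 4.1, the device arm has 24 weekly ePROs, of which the first is baseline: 24 − 1 = 23 post-baseline assessments of four instruments. The horizon from the week 1 visit to the week 24 visit is H = 23 weeks. Controls have 3 post-baseline assessments, at weeks 4, 8 and 12.

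**2. Responder-only mean against restricted mean.** Assume a constant response rate, with a share F responding by H.
- rate λ = −ln(1 − F)/H
- responder-only mean = 1/λ − H(1 − F)/F
- restricted mean (never-responders contribute H) = F/λ

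For F = 0.30: 1/λ = 23/0.3567 = 64.48. Responder-only mean = 64.48 − 23 × 0.7/0.3 = 64.48 − 53.67 = 10.8. Restricted mean = 0.3 × 64.48 = 19.3.

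| F | 1/λ | H(1 − F)/F | Responder-only mean, weeks | Restricted mean, weeks |
|---|---|---|---|---|
| 0.30 | 64.48 | 53.67 | 10.8 | 19.3 |
| 0.50 | 33.18 | 23.00 | 10.2 | 16.6 |
| 0.70 | 19.10 | 9.86 | 9.2 | 13.4 |
| 0.90 | 9.99 | 2.56 | 7.4 | 9.0 |

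From 30% to 90% response the responder-only mean falls by 3.4 weeks (31%) and the restricted mean by 10.4 weeks (54%). Between 30% and 50% the responder-only mean moves by only 0.6 weeks.

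The constant rate matters. If all responses fell evenly in weeks 1 to 6, the responder-only mean would be 3.5 weeks at any response share. The restricted mean would be 0.2 × 3.5 + 0.8 × 23 = 19.1 weeks at 20% response and 0.9 × 3.5 + 0.1 × 23 = 5.5 weeks at 90%.

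**3. Chance response.** Stable participants were simulated with no device effect and no drift. All inputs are assumptions:
- reliability 0.70 to 0.95, and week-to-week error correlation 0.5 to 0.9
- low to high baselines in the non-primary domains
- SDs of 2.0 (PEG), 4.5 (GAD-7), 5.0 (PHQ-9) and 3.3 (PROMIS raw score)
- between-domain correlation 0.4

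With those SDs, 15% to 98% of stable participants meet the event at least once by week 24. The lower end depends on the SDs. In the least noisy setting (reliability 0.95, error correlation 0.9, high baselines), multiplying the SDs by 0.7 gives about 2%, and by 1.3 about 32%. The defensible range is therefore about 2% to 98%.

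**4. Precision of a two-arm comparison.** The 95% CI half-width for a difference in proportions is 1.96 × √(2p(1 − p)/n), largest at p = 0.5. Section 4.0 plans 100 to 200 subjects randomised 1:1, so n = 50 to 100 per arm.
- n = 50: 1.96 × √(0.5/50) = 0.196, about 20 points
- n = 100: 1.96 × √(0.5/100) = 0.139, about 14 points

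**The case against.** The strongest reply is that handling of non-responders belongs in a statistical analysis plan, which is not at hand, and that a restricted mean is still a mean time. The protocol never says that responders alone are averaged. The second part of this stands: the responder-only figures show what one natural reading would give, not what the protocol prescribes. But the protocol itself chose the statistic, and as written it is not defined for everyone in the arm.

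A second reply is that a device-arm description is coherent, because time from starting treatment has no direct control counterpart, and that 8.1 and item 2 of 8.2 already compare the arms. This also stands in part. Controls need no time-to-response figure, but a 30% response proportion at shared visits is available and is the natural yardstick for chance response.

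Third, the 98% end of the chance range proves little, because the low end is about 2%. That is correct.

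A reader might infer that the single-visit event contradicts the persistence rule in section 4.1, footnote 3 ("Upon having three consecutive weeks of primary symptom reduction of" at least 70%). It does not. That rule governs continuation of device therapy, at another threshold and for another purpose, and 8.3 already separates initial from sustained benefit.

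**Conclusion.** The point holds as a minor one. The protocol fixes a mean that is undefined for never-responders, and plans no 30% response figure for controls although the questionnaires that would supply it are scheduled.

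The 10.8 to 7.4 week contrast rests on a constant response rate and on averaging responders only, which is not stated. Even then the mean does shorten by 31% between 30% and 90% response, so it is weakly sensitive to the response share, not blind to it. The size of chance response is unknown: the protocol gives no reliability, SD or baseline figures.

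Two stronger readings are not supported. One is that most reported benefit would be noise; nothing in the protocol establishes that. The other is that the effectiveness conclusion is compromised; this endpoint is descriptive, and the between-arm comparison of scores in 8.1 does not use it.

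**What to change.** 1. In 8.2 item 1 and the second bullet of 8.3, replace the mean with a Kaplan-Meier curve and the restricted mean time from the week 1 visit to the week 24 visit. Censor participants who have not reached a 30% fall at their last ePRO. Keep the any-of-four event as defined; it matches the objective in section 2.0.
2. Add to 8.2 the proportion with at least a 30% reduction from baseline in any domain at weeks 4, 8 and 12, in both randomised arms, with the difference and its 95% CI. Use the value at each of these shared visits alone. Counting a response at any visit so far would set weekly device-arm assessments against three control assessments and favour the device arm by schedule.

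The cost is a change of wording and a little programming, with no new visits or data. The reported time will be longer than a responder-only mean. The difference in proportions will be imprecise, with a half-width of up to about 20 points at 50 per arm or 14 at 100 per arm.

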3.0 STUDY PARTICIPANT SELECTION CRITERIA

3.1 Inclusion Criteria

- Participant is at least 18 years of age
- Participant presents with one or more of the following symptoms: chronic pain, anxiety, depression, and/or sleeplessness
- Participants must score greater than or equal to a 5/10 for their primary symptom score on the Baseline Symptom Questionnaire
- Patient's chosen primary symptom must have an available accrual slot for the participant. If patient scores greater than or equal to a 5/10 for a second symptom, they can be selected to accrue to another symptom slot.
- Participant has signed the Informed Consent Form

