4.0 STUDY PROTOCOL

The Nu-V3 Clinical Study is a randomized, open-label study using the Nu-V3 cranial nerve stimulation treatment device in patients with chronic pain, anxiety, depression, and/or sleeplessness. Study participants are those who have signed the informed consent form, met the inclusion and exclusion criteria, and are enrolled in the study at one of multiple sites.

Subjects randomized to receive the Nu-V3 treatment will undergo the following regimen:

- At the baseline visit, patients will be asked to complete study questionnaires (Appendix 11) regarding all of the following symptoms: chronic pain, anxiety, depression, and/or sleeplessness, as well as their quality of life, active medications, medical history, and demographical information. The subject's primary symptom of concern will also be notated at baseline, for later assessment of continuation after week 12.
- At each subsequent visit, patients will be asked to complete study questionnaires regarding all the following symptoms: chronic pain, anxiety, depression, and/or sleeplessness, as well as their activity level and quality of life.
- The sessions will begin with the Nu-V3 device being clipped on the ear and three small pads (non-invasive) adhered to the surface of the ear. Each Nu-V3 device lasts for up to 28 days with a change in the pads approximately 7 days into the treatment.
- Each session takes approximately 15-20 minutes. The placement of the device takes approximately 5 minutes, and the remaining time is spent verifying ePRO form completion, and evaluating the patient for all device effects.
- The Nu-V3 device is mobile and is worn externally on the left ear 24 hours a day during treatment, fitting comfortably behind the ear. An electrical signal is sent to

the external ear through coated wire leads attached to the device and adhesive pads which attach to three sites on the ear.

- Participants should be able to perform their typical day-to-day activities while wearing the device. They may shower while wearing the Nu-V3 device, if they do not get the device wet and use the small disposable ear covers that are provided for them.
- In the event the Nu-V3 gel pads are inadvertently removed or the device comes off, the participant will contact the site coordinator. The participant is encouraged to adjust the device placement as needed for comfort.
- Patients should not change their existing forms of treatment or medications without discussion with the study investigator.

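### Mean percentage change per instrument (8.2 item 2) is undefined at a zero baseline and over-weights near-zero baselines, and the entry criteria allow both

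*Protocol*

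**What the plan says.** Section 8.2, secondary effectiveness endpoint 2, commits both arms to one summary: "the study will report the mean percentage change in symptoms severity from initiation to 12 and 24 weeks for each instrument". It names arms, times and instruments. It gives no formula, does not say which patients are averaged for each instrument, and has no rule for a baseline of zero.

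Four other provisions determine what baselines can occur:

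- Section 3.1 admits a patient with a single symptom: "Participant presents with one or more of the following symptoms: chronic pain, anxiety, depression, and/or sleeplessness".
- The only severity floor, also in Section 3.1, is on the chosen symptom and on a different form: "Participants must score greater than or equal to a 5/10 for their primary symptom score on the Baseline Symptom Questionnaire". Appendix 9 shows that form, which is separate from the four outcome instruments.
- Section 4.0 has every patient answer for every symptom. At baseline, "patients will be asked to complete study questionnaires (Appendix 11) regarding all of the following symptoms: chronic pain, anxiety, depression, and/or sleeplessness", with equivalent wording for the control arm. At later visits in both arms, "patients will be asked to complete study questionnaires regarding all the following symptoms".
- Section 8.1 lets three of the instruments start at zero. PEG is the average of three items scored 0 to 10. For GAD-7, "Each item is scored on a four-point Likert scale, and values range from 0" up to 3, and seven items are summed. PHQ-9 sums nine items on the same 0 to 3 scoring. No scoring is given for the PROMIS sleep form.

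**The concern.** Each instrument will be completed by people enrolled for another symptom. A patient enrolled for pain may score 0 on GAD-7, where percentage change has no value, or 1 to 3, where a single point is 100% to 33%. The measure is also lopsided. It cannot fall below -100%, but from a GAD-7 baseline of 1 it can reach 100 x (21 - 1)/1 = +2000%.

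The patients with least of a symptom therefore have most influence on the figure meant to describe how that symptom changed. At stake is a reported secondary result that is unstable, is undefined for some eligible patients, and can point the opposite way to the change in scores.

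**Working it through.** The protocol gives no figure for this endpoint, so there is nothing to reproduce. The check uses its scales and its arm size (100-200 patients randomized 1:1, so 50-100 per arm).

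**Formulas.** With baseline b and follow-up f for each of n patients:

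- Mean percentage change: (1/n) x sum of 100(f - b)/b. Each patient's point change is multiplied by 100/b.
- Mean point change: (1/n) x sum of (f - b).
- Percentage of means: 100 x (mean change / mean baseline).

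**Zero baseline.** (f - 0)/0 is undefined. This can occur on PEG, GAD-7 and PHQ-9. It cannot be shown for PROMIS, whose scoring is not given.

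**Weight of one point.**

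- GAD-7: 100/1 = 100% at baseline 1; 100/12 = 8.3% at baseline 12. The ratio is 12.
- PEG: the smallest non-zero score is 1/3, so one point is 300%; at baseline 6 it is 100/6 = 16.7%. The ratio is 18.

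**Sign, in a GAD-7 arm of 50 (illustrative scores).** Suppose 45 patients fall from 12 to 8 (-33.3% each) and 5 rise from 1 to 5 (+400% each).

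- Mean percentage change: (45 x -33.3 + 5 x 400)/50 = (-1500 + 2000)/50 = +10%.
- Mean point change: (45 x -4 + 5 x 4)/50 = -160/50 = -3.2.
- Mean baseline: (45 x 12 + 5 x 1)/50 = 10.9. Percentage of means: 100 x (-3.2/10.9) = -29.4%.

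Varying the number at baseline 1 and their rise, with everyone else falling from 12 to 8:

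| Patients at baseline 1 | Rise (points) | Mean % change | Mean point change |
|---|---|---|---|
| 1 | 4 | -24.7% | -3.84 |
| 5 | 3 | 0.0% | -3.3 |
| 5 | 4 | +10.0% | -3.2 |
| 10 | 1 | -6.7% | -3.0 |
| 10 | 2 | +13.3% | -2.8 |
| 10 | 4 | +53.3% | -2.4 |

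If a fraction p sits at baseline 1 and rises by r points, the mean percentage change is zero when 100pr = 33.3(1 - p), that is r = (1 - p)/(3p). This gives r = 3 at p = 10% and r = 1.3 at p = 20%. At p = 2% (one patient in 50), r = 16.3.

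**Precision and frequency (simulation, all inputs assumed).** GAD-7, 50 patients per arm, 4000 runs per setting. Symptomatic patients had mean 13 and SD 3.5; low-symptom patients were exponential with mean 2. Proportional benefit was 20% or 30%, measurement error SD was 1.5 or 2.5 points, and zero baselines were left out of the percentage. Ranges run over the four benefit and error settings.

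| Low-symptom share | Baseline of zero | SD of arm's mean % change | Arms with positive mean % but negative mean point change |
|---|---|---|---|
| 0% | 0.1-0.2% | 2.7-5.4 | 0-1.2% |
| 25% | 7.2-8.5% | 5.8-9.0 | 0-6.8% |
| 50% | 14.0-16.6% | 8.3-12.5 | 0.4-12.1% |
| 75% | 21.0-24.9% | 10.8-16.1 | 1.0-18.0% |

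From a 0% to a 75% share, the SD rises about 3- to 4-fold (for example 2.8 to 11.2, and 5.4 to 16.1). The runs did not record the SD of the point change, so this is not a head-to-head comparison of precision.

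**The case against.** Several counter-arguments have weight.

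- **Patient set.** Item 2 does not say that all patients are averaged on every instrument. Section 4.0 enrols patients into symptom cohorts and bases analyses at 6, 12, 18 and 24 weeks on them, which includes both of item 2's time points. That sentence concerns interim analyses, so it does not settle item 2. Restriction to cohorts would reduce the problem but not remove it, because the 5/10 floor is not on the analysed instrument.
- **Formula.** The phrase could mean the percentage change of the arm mean, and the problem would then largely vanish. Averaging individual percentages is the more natural reading, and the text does not say otherwise.
- **Zero baselines.** A reader might infer that patients at zero are dropped. The protocol does not say so, and a SAP could supply a rule. Such a rule would not change the weight given to baselines of 1 to 3.
- **Size.** A reader might infer that the endpoint will usually show worsening where there is improvement, or that a few patients will decide the comparison between arms. Neither is supported. One low-baseline patient in 50 leaves the mean at -24.7%, reversal was uncommon in most simulated settings, and no between-arm calculation was made. Section 1.1 says the symptoms often cluster, which would lower the share of low baselines.
- **Consequence.** Item 2 is a reported secondary quantity with no test or success rule attached. The primary hypothesis is already in mean severity scores.
- **The 30% rule.** It is tempting to extend the point to Section 8.3: "Benefit is defined as a reduction of at least 30% of symptoms in at least one of" the four symptoms. A one-point fall from a GAD-7 score of 3 would meet it. But counting any domain follows the Section 2.0 objective of relief from one or more symptoms, and limiting it to the enrolled symptom would redefine the endpoint. That trade-off is debatable and is not part of this point.

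**Conclusion.** The point holds for the metric written in item 2, read as an average of individual percentages over all patients. Two consequences follow from the protocol's own scales and entry criteria. Percentage change is undefined at a zero baseline on PEG, GAD-7 and PHQ-9, and near-zero baselines carry up to 12 times (GAD-7, 1 against 12) or 18 times (PEG, 0.33 against 6) the weight of a symptomatic patient's score.

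How imprecise the mean becomes, and how often its sign reverses, depends on the share of low baselines, which the protocol does not give. Reversal needs roughly 10-20% of an arm near zero and rising by 2-4 points when the others improve by a third. It is possible, not typical. The metric should be changed, but no primary conclusion rests on it.

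**What to change.** In Section 8.2 item 2, replace mean percentage change with the mean change in scale points per instrument by arm, adjusted for the baseline score. If a percentage is wanted for readability, report 100 x (mean change / mean baseline) per arm. Both keep the right sign in the worked example (-3.2 points, -29.4%), and neither requires dividing by an individual's baseline. They work whether item 2 covers all patients or only the symptom cohort.

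The cost is a change of wording. The scores are already collected, no patients or visits are added, and item 2 comes into line with the primary hypothesis. The downside is that any percentage reported is no longer the average of individual patients' percentages, and the text should say so.
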